11.1.4 Allocation of TEAEs to Treatment Periods

TEAEs will be allocated to treatment periods according to the time of onset of the adverse event:

• *adverse event in the open-label treatment period* – an adverse event that starts or increases in intensity after the date of Baseline II and at or before the date of the last protocol-

LU Study Number: 14861B Trial Site Number: Study Level Pluto ID: CLI 00933680

- specified contact in the study for patients not continuing into the open-label treatment period with memantine, and at or before the date of Baseline III for patients in the APES2.
- adverse event in the open-label treatment period with memantine an adverse event that starts or increases in intensity after the date of Baseline III and at or before the date of the last protocol-specified contact in the study.

Note, the completion Visit in the lead-in studies are the same as the Baseline II Visit in the extension study, and adverse events ongoing or starting at Baseline II and not increasing intensity will only be reported in the lead-in study.

All tables and listings will be presented separately for adverse events in the open label treatment period, and the open label treatment period with memantine.

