16.2 Analysis Sets

The following analysis sets will be used to analyse and present data:

- *all-patients-treated set* (APTS) all patients who took at least one dose of IMP in the open label treatment period (initial 28-week period).
- *all-patients-treated set 2* (APTS2) all patients who took at least one dose of both IMP and memantine in the open-label treatment period with memantine (substudy).

Each patient will be classified according to this definition at a Classification Meeting held after all the data have been entered in the study database and verified.

All descriptive statistics and statistical analyses in the open-label treatment period (initial 28week period) will be based on the APTS, and all analyses in the open-label treatment period with memantine (substudy) will be based on APTS2. Listings will be based on all patients entering the treatment period.

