• Adverse events (AEs)

LU Study Number: 14861B Trial Site Number: Study Level Pluto ID: CLI 00933680

- Clinical safety laboratory tests
- Vital signs
- Weight
- Electrocardiograms (ECGs)
- Columbia Suicide Severity Rating Scale (C-SSRS)

Other endpoints

• Plasma concentrations of idalopirdine and memantine in the open label treatment period with memantine

4 Analysis Sets

The following analysis set will be used to analyse and present data:

The sets of patients to be analysed are defined as follows:

Open label treatment period

- all-patients-enrolled set (APES) all patients enrolled in the open-label treatment period
- *all-patients-treated set* (APTS) all patients in APES who took at least one dose of IMP in the open-label treatment period

Open label treatment period with memantine

- *all-patients-enrolled set 2* (APES2) all patients who enrolled in the open-label treatment period with memantine
- *all-patients-treated set 2* (APTS2) all patients in APES2 who took at least one dose of IMP or memantine in the open-label treatment period with memantine.

Each patient will be classified according to these definitions based on information in data, and no Classification Meeting will be held.

If not otherwise specified, tables, figures, and listings will be based on the APTS for the open-label treatment period, and on APTS2 for the open-label treatment period with memantine.

5 Descriptive Statistics

Unless otherwise specified, summary statistics (n, arithmetic mean, standard deviation [SD], median, lower and upper quartiles, minimum and maximum values) will be presented for continuous variables, and counts and, if relevant, percentages will be presented for categorical variables.

Tables and figures for the open label treatment period will be presented by lead-in treatment group and in total.

LU Study Number: 14861B Trial Site Number: Study Level Pluto ID: CLI 00933680

Unless otherwise specified, data listings will include lead-in treatment group (placebo or idalopirdine [dose 10mg, 30mg, or 60mg]), site, patient screening number (from lead-in study), and lead-in study-Baseline I information on sex, age, race, and weight.

6 Patient Disposition

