11.1.5 All Adverse Events

All adverse events will be listed for the APES and APES2.

An overview of the PYE, numbers, and percentages of patients with TEAEs, serious adverse events (SAEs), adverse events leading to withdrawal, or patients who died will be provided. For TEAEs, SAEs, and adverse events leading to withdrawal, the total number of events will be included.

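### Adverse events after Baseline III in patients who enrol in the memantine substudy but take neither drug there fall into no summary table

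*SAP*

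**What the plan says.** SAP 11.1.4 allocates treatment-emergent events to periods by date. For a patient who does not go on to the substudy, the open-label period runs to the last protocol-specified contact. For substudy enrollees it ends earlier: "at or before the date of Baseline III for patients in the APES2". The memantine period takes "an adverse event that starts or increases in intensity after the date of Baseline III", up to the last protocol-specified contact. The same section presents the two periods separately.

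SAP section 4 defines the sets. APES2 is "all patients who enrolled in the open-label treatment period with memantine". APTS2 is "all patients in APES2 who took at least one dose of IMP or memantine in the open-label treatment period with memantine". Unless otherwise specified, tables, figures and listings are based on the APTS for the open-label period, "and on APTS2 for the open-label treatment period with memantine".

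SAP 11.1.5 makes one exception: "All adverse events will be listed for the APES and APES2". The summaries in 11.1.5 to 11.1.11, and the listings of deaths, SAEs and events leading to withdrawal in 11.1.7 to 11.1.9, name no other set. SAP section 17 declares one change from the protocol, which concerns the C-SSRS.

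**The concern.** The cut-off is tied to enrolment and the later tables are tied to dosing. A patient who signs the substudy consent, is enrolled at Visit 6 and then takes neither drug lies between the two rules. That patient has had up to 28 weeks of idalopirdine and is in the APTS. The protocol counts as treatment-emergent anything that starts between first dose and the last protocol-specified contact (Protocol 16.9.1), so these events belong in the safety evaluation.

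An otherwise identical patient who did not enrol has the same events tabulated to last contact. The only difference is enrolment in the substudy. Safety and tolerability are the primary objective of both periods, and at the follow-up visit the only new events collected are SAEs (Protocol 8.5; Panel 2 note k; Panel 3 note g). What drops out of the tables is therefore small in number but mostly serious in kind.

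**Working it through.** The plan states no figure for this point, so there is nothing to reproduce. The check is to run each type of patient through the rules, then to size the gap.

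**Can such a patient exist?** Yes. Consent and eligibility are settled at Visit 6, and the first substudy dose is due the next day (Protocol 6.1 and 8.3).

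**Where does an event after Baseline III go under the SAP?**

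| Patient | Open-label window ends | In APTS2 (SAP)? | Event in a summary table? |
|---|---|---|---|
| Not enrolled in substudy | Last contact | No | Yes, open-label |
| Enrolled, idalopirdine only | Baseline III | Yes | Yes, memantine period |
| Enrolled, memantine only | Baseline III | Yes | Yes, memantine period |
| Enrolled, both drugs | Baseline III | Yes | Yes, memantine period |
| Enrolled, neither drug | Baseline III | No | **No** |

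Only the last row is uncovered. No pooled table recovers it, because the periods are presented separately. The default set also governs listings, so the SAE, death and withdrawal listings for the memantine period would omit these events. The all-AE listing on APES and APES2 keeps them.

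**Size.** Inputs:

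- Number of enrollees who take neither drug: not in the documents. Assumed 0 to 5 of the 100 planned.
- SAE risk: 9.7% on idalopirdine in the phase II study (Protocol 1.1.3.3). That study is described as lasting 6 months, taken here as about 24 weeks. The dose there was 90 mg/day, so this is only a rough guide.
- Time at risk: taken as the 4-week safety follow-up.
- Constant hazard.

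Four-week risk per patient: 1 − (1 − 0.097)^(4/24) = 1 − 0.903^0.1667 = 0.017, or about 1.7%. Taking 6 months as 26 weeks gives 1 − 0.903^(4/26) = 0.016, so the choice hardly matters.

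Expected patients with an untabulated SAE: 0 × 0.017 = 0 at the lower end and 5 × 0.017 ≈ 0.08 at the upper end.

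**After the change.** If the cut-off refers to APTS2 and everyone else in the APTS runs to last contact, the last row becomes: window ends at last contact, event tabulated in the open-label period. All five rows are then covered.

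**The case against.** The strongest reply is that this is a drafting matter with almost no numerical consequence. The patients have just completed 28 weeks, agreed to continue and been given new supplies; the number who then take neither drug may be 0 or 1. The all-AE listing covers APES2 and shows seriousness, outcome and date of death (SAP 11.1.1), and the disposition table reports the size of each set (SAP 6.1), so a careful reader could find the patients. All of this stands, and it is why the point is minor.

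Two further arguments carry less weight. One is that an undosed enrollee could be classed as not continuing, which would run the open-label window to last contact. The explicit APES2 clause in the same sentence contradicts that reading, and two programmers could resolve it differently. The other is that Protocol 16.2 bases listings on all patients entering the period. The SAP's default of APTS2 for listings departs from this without saying so, and the protocol rule would not repair the tables in any case.

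A reader might also infer a much larger loss by noting that the protocol defines APTS2 as "all patients who took at least one dose of both IMP and memantine". On that definition, a patient who continued idalopirdine without memantine would seem to lose up to 24 weeks of on-drug events: 1 − 0.903^(28/24) ≈ 11% SAE risk over 28 weeks, or about 0.6 patients among five. The documents do not support this. It joins the protocol's analysis set to a cut-off that exists only in the SAP. The protocol has no APES2 and leaves the division into periods to the SAP, and under the SAP's own definition such a patient is in APTS2 and is tabulated.

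**Conclusion.** The gap is real on the text and narrow. Events after Baseline III in patients who enrolled in the substudy and took neither drug there are in no summary table and, by default, in none of the SAE, death or withdrawal listings. It would go too far to say that they are lost from the report, since the all-AE listing retains them.

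The expected size is 0 to 0.08 SAE patients. This rests on an assumed 0 to 5 affected enrollees, the phase II SAE risk at another dose, a constant hazard and a 4-week period at risk. Severity is minor. It still deserves correction because the rule treats like patients differently, concerns mostly serious events in the main safety summaries, and costs almost nothing to change. The differing APTS2 definitions in protocol and SAP are a separate inconsistency and do not enlarge this one.

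**What to change.** In SAP 11.1.4:

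- make the Baseline III cut-off apply to patients in the APTS2 instead of the APES2;
- run the open-label window to the last protocol-specified contact for every other APTS patient;
- restrict the definition of a memantine-period event to APTS2 patients, so that no event is allocated to both periods.

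In SAP section 8, align the concomitant-medication cut-off, which uses the same APES2 wording, so that events and medications share one boundary.

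Separately, reconcile the APTS2 definition between Protocol 16.2 (both drugs) and SAP section 4 (either drug), and record the outcome in SAP section 17. The window change closes the gap under either definition.

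The cost is a few phrases in the SAP and the matching programming of the period flags. No new data are needed.

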11.1.5 All Adverse Events

All adverse events will be listed for the APES and APES2.

An overview of the PYE, numbers, and percentages of patients with TEAEs, serious adverse events (SAEs), adverse events leading to withdrawal, or patients who died will be provided. For TEAEs, SAEs, and adverse events leading to withdrawal, the total number of events will be included.

11.1.6 Treatment-emergent Adverse Events

The following summaries will be provided:

- TEAEs by SOC and preferred term (only for open label treatment period)
- TEAEs by preferred term
- TEAEs with an incidence >3% by preferred term
- causally related TEAEs by SOC and preferred term TEAEs by intensity (*mild/moderate/severe*) and preferred term
- causally related TEAEs by intensity and preferred term (only for open label treatment period)

11.1.7 **Deaths**

All adverse events for patients who died will be listed.

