16.9 Safety Analyses

Safety tables will be presented for each treatment period separately by treatment group (placebo or idalopirdine all doses pooled) in the lead-in study, and in total.

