16.9.1 Analysis of Adverse Events

Adverse events will be classified according to when the adverse event started:

• *treatment-emergent adverse event* (TEAE) – an adverse event that starts on or after the date of first dose of IMP in the extension study and prior to the last protocol-specified contact with that patient. TEAEs may be divided into study periods (these will be defined in the Statistical Analysis Plan).

Adverse events, sorted by system organ class (SOC) and preferred term, will be summarised by treatment group in the lead-in study and in total.

If relevant, incidence and prevalence in the lead-in study and in the open-label treatment period (initial 28-week period) for selected preferred terms will be presented by treatment group in the lead-in study.

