11.1.9 Adverse Events Leading to Withdrawal

All adverse events leading to withdrawal will be listed.

TEAEs leading to withdrawal will be summarised by preferred term. For the open label treatment period the summary will also be generated by SOC and preferred term.

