11.1.11 Adverse Events of Special Interest

The following standardized MedDRA queries (SMQ) will be summarised in total and by preferred term:

- Convulsions (narrow scope)
- Drug-related hepatic disorders -comprehensive search
- Haemorrhages (broad scope)

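### The SAP drops the all-cause TEAE table by system organ class for the memantine substudy, contrary to protocol 16.9 and 16.9.1, and does not declare the change

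*SAP*

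**What the plan says.** Protocol 16.9 sets the general rule: "Safety tables will be presented for each treatment period separately by treatment group". Protocol 16.9.1 then says: "Adverse events, sorted by system organ class (SOC) and preferred term, will be summarised by treatment group in the lead-in study and in total". Neither sentence is limited to the 28-week period.

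SAP 11.1.4 keeps the same rule for adverse events: "All tables and listings will be presented separately for adverse events in the open label treatment period, and the open label treatment period with memantine". The list of TEAE summaries in SAP 11.1.6, however, gives the all-cause table as "TEAEs by SOC and preferred term (only for open label treatment period". In the same list, "causally related TEAEs by SOC and preferred term" carries no such limit. In SAP 11.1.8 and 11.1.9, SAEs and TEAEs leading to withdrawal are summarised by preferred term in both periods, and SOC is added for the first period only: "For the open label treatment period the summary will also be generated by SOC and preferred term".

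SAP section 17, which records changes from the protocol's analyses, names only the C-SSRS summary.

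**The concern.** The substudy's primary objective (protocol 2.1, SAP 1.1) is the safety and tolerability of idalopirdine, memantine and donepezil given together, in about 100 patients. In a group of that size, an effect spread over several related preferred terms can sit in rows of one or two patients each and be visible only when the terms are grouped. The all-cause SOC table does that grouping without depending on anyone's causality judgement. The SAP produces it for the period before memantine and not for the period with it. Protocol 3.2 nevertheless justifies the design partly by comparing safety within the same patient before and after memantine is added. A reader of the protocol would expect the table, and section 17 gives no notice that it has gone.

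**Working it through.** **1. What the SAP produces in each period (SAP 11.1.5 to 11.1.11)**

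| Output | 28-week period | Memantine substudy |
|---|---|---|
| All TEAEs, SOC and preferred term | yes | **no** |
| All TEAEs, preferred term | yes | yes |
| TEAEs above 3%, preferred term | yes | yes |
| Causally related TEAEs, SOC and preferred term | yes | yes |
| TEAEs by intensity, preferred term | yes | yes |
| SAEs and withdrawal TEAEs, preferred term | yes | yes |
| SAEs and withdrawal TEAEs, SOC and preferred term | yes | no |
| Three SMQs | yes | yes |
| Listing of all AEs | APES | APES2 |

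The first row is what protocol 16.9 and 16.9.1 commit to for both periods. The protocol names no separate SOC table for SAEs or withdrawal events.

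**2. Whether the remaining outputs replace the missing table**

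- *Causally related TEAEs by SOC.* Protocol 10.1.2 rates causality against the IMP and classes an event due to another drug as not related. Protocol 6.2 makes idalopirdine the IMP and memantine a base treatment. An event attributed wholly to memantine is therefore not counted. One the investigator considers possibly due to idalopirdine still is.
- *SMQs.* SAP 11.1.11 says "The following standardized MedDRA queries (SMQ) will be summarised in total and by preferred term", then names convulsions, drug-related hepatic disorders and haemorrhages. Other event classes are not grouped.
- *The table above 3%.* With n = 100, 3/100 = 3% does not exceed 3%, so a term needs at least 4 patients to appear.
- *Listings.* All AEs are listed for APES2 (SAP 11.1.5), by patient and with preferred term. SOC is not among the fields named in SAP 11.1.1, so a class count needs the terms mapped and the patients counted by hand.

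**3. Why preferred-term rows cannot be added**

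A patient with two terms in one SOC counts in two rows but once in the class. For terms with counts x1, ..., xk, the class total lies between max(xi) and the sum of the xi (capped at n). The rows do not say where.

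**4. Illustration on the plan's own scale**

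The plan's precision table (protocol 16.11, SAP 15) gives one-sided 90% upper limits at n = 100. The exact limit p solves P(X ≤ x | 100, p) = 0.10, which is the 0.90 quantile of Beta(x + 1, 100 − x).

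| Patients with event | 0 | 1 | 2 | 3 | 4 | 5 | 10 |
|---|---|---|---|---|---|---|---|
| Plan | 2.3% | 3.9% | 5.3% | 6.6% | 7.9% | 9.1% | 15.0% |
| Recomputed | 2.28% | 3.83% | 5.23% | 6.56% | 7.83% | 9.08% | 14.99% |

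The plan's figures are reproduced when rounded up.

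Now assume five preferred terms in one SOC, each in 2 of 100 patients. These counts are not from the documents.

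- Each row reads 2%, upper limit 5.23%. None enters the table above 3%.
- Full overlap: max = 2 patients, 2%, upper limit 5.23%.
- No overlap: 5 × 2 = 10 patients, 10%, upper limit 14.99%.

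The same five rows fit both totals.

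**The case against.** The strongest reply is that this is one descriptive table in a single-arm substudy, and the data behind it are fully listed. Much of that stands.

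- A reader might infer that class-level risk of the triple combination goes unreported. The SAP does not support that. The causally related SOC table and the SMQ totals are kept, SAP 11.3.3 adds post-Baseline III liver tables, joint criteria and plots, and the overview in 11.1.5 counts patients with any TEAE, SAE or withdrawal event.
- A reader might infer that class counts are lost. They are not. The APES2 listings show each patient's terms, and about 100 patients can be counted by hand.
- A reader might infer that the SOC tables of SAEs and withdrawal events are also a broken protocol commitment. Protocol 16.9.1 speaks of adverse events generally, so adding SOC detail for one period only is not a departure. The gain would also be limited. At the rates reported from the phase II AD study in protocol 1.1.3.3 (9.7% with SAEs, 15% withdrawn for TEAEs), 100 patients would give about 10 and 15, and each event is listed anyway. That study used 90 mg/day and is only a rough guide.
- The illustration rests on assumed counts. The documents give no term-level rates for the substudy.

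The reply does not remove the main point. The all-cause table is promised by the protocol, dropped without notice, and not replaced by a table that depends on attribution to idalopirdine.

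**Conclusion.** The point holds for one table. SAP 11.1.6 departs from protocol 16.9 and 16.9.1 by limiting the all-cause TEAE table by SOC to the 28-week period, and section 17 does not declare it. For the substudy, all-cause incidence by class is not tabulated, although it can be worked out from the listings. This rests on reading the two protocol sentences together, which is their plain sense because 16.9.1 sits under 16.9 and sets no period limit.

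The size cannot be fixed from the documents. In the illustration, the same preferred-term output is compatible with 2% or 10% of patients affected in a class. The consequence is a less readable report on a primary objective. No estimate or test becomes invalid.

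Restoring the table would not by itself deliver the within-patient comparison of protocol 3.2, because the 28-week table covers all of APTS and not only those who go on to memantine. It would supply the with-memantine side at class level.

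**What to change.** In SAP 11.1.6, delete the parenthesis that limits the TEAE table by SOC and preferred term to the open-label treatment period, so that it is also produced for APTS2. If the sponsor prefers to keep the restriction, section 17 should declare it and give the reason; that would cure the silence but not the missing table.

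Optionally, for consistency, extend the SOC summaries in 11.1.8 and 11.1.9 to the substudy.

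The cost of the main change is one wording edit and one more run of a table already specified for the 28-week period. The optional change adds two further runs. No new data are needed.

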11.1.8 Serious Adverse Events

All SAEs will be listed.

Treatment-emergent SAEs will be summarised by preferred term. For the open label treatment period the summary will also be generated by SOC and preferred term.

LU Study Number: 14861B Trial Site Number: Study Level Pluto ID: CLI 00933680

11.1.9 Adverse Events Leading to Withdrawal

All adverse events leading to withdrawal will be listed.

TEAEs leading to withdrawal will be summarised by preferred term. For the open label treatment period the summary will also be generated by SOC and preferred term.

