- 3. The patient takes or has taken disallowed recent or concomitant medication (specified in Appendix II) or it is anticipated that the patient will require treatment with at least one of the disallowed concomitant medications during the study.
- 4. The patient's donepezil treatment is likely to be interrupted or discontinued during the study.
- 5. The patient is receiving therapy with another AChEI or memantine.
- 6. The patient has clinically significant abnormal vital signs at the Completion Visit in the lead-in study considered a potential safety risk by the Investigator.
- 7. The patient has a moderate or severe on-going adverse event from the lead-in study considered a potential safety risk by the investigator.
- 8. The patient has been tested positive for hepatitis B surface antigen (HBsAg), or hepatitis C virus/antibodies (anti-HCV), AND had abnormal ALT, AST or bilirubin in the lead-in study.
- 9. The patient has been tested positive for hepatitis B surface antigen (HBsAg), or hepatitis C virus/antibodies (anti-HCV) for the first time within the last 6 months prior to the Completion Visit in the lead-in study.
- 10. The patient has one or more clinical laboratory test values outside the reference range, based on the latest blood and urine sample results, available at the Completion Visit in the lead-in study, that are of potential risk to the patient's safety, or the patient has according to the latest available blood sample:
 - a serum creatinine value >1.5 times the upper limit of the reference range, or
 - a serum total bilirubin value >1.5 times the upper limit of the reference range, or
 - a serum alanine aminotransferase (ALT) or aspartate aminotransferase (AST) value >1.5 times the upper limit of the reference range.
- 11. The patient has, based on the latest ECG results, available at the Completion Visit in the lead-in study:
 - an abnormal ECG that is, in the investigator's opinion, clinically significant, or
 - a heart rate <45 beats per minute, or
 - a PR interval >280 ms, or
 - a QRS interval >150 ms, or
 - a QTcF interval >480 ms (based on the Fridericia correction where $QTcF = QT/RR_{0.33}$)

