11.1.3 Classification of Adverse Events

Adverse events will be classified according to the time of onset of the adverse event: treatment-emergent adverse event (TEAE) – an adverse event that starts or increases in intensity after the date of Baseline II.

An adverse event is considered causally related to the use of the IMP when the causality assessment by the investigator is *probable* or *possible*.

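### Preferred-term summaries of withdrawals and SAEs take only TEAEs, placed by onset or worsening, so an earlier-onset event that causes withdrawal at unchanged intensity is missing or in the wrong period

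*SAP*

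**What the plan says.** SAP 11.1.3 defines a TEAE as "an adverse event that starts or increases in intensity after the date of Baseline II". SAP 11.1.4 then states that "TEAEs will be allocated to treatment periods according to the time of onset of the adverse event". An event belongs to the memantine period only if it "starts or increases in intensity after the date of Baseline III". For substudy patients, anything dated on or before Baseline III stays in the initial period. The same section adds that "adverse events ongoing or starting at Baseline II and not increasing intensity will only be reported in the lead-in study".

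The summaries build on these definitions. For withdrawals, "TEAEs leading to withdrawal will be summarised by preferred term" (SAP 11.1.9). For serious events, "Treatment-emergent SAEs will be summarised by preferred term" (SAP 11.1.8). In the 28-week period both are also given by SOC. Neither leading to withdrawal nor becoming serious makes an event treatment-emergent or changes its period.

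Other outputs carry no such limit:
- SAP 6.2 tabulates withdrawals from each period by reason.
- SAP 11.1.8 and 11.1.9 plan listings of all SAEs and all AEs leading to withdrawal.
- The overview in SAP 11.1.5 names SAEs and AEs leading to withdrawal without restricting them to TEAEs.
- SAP 11.1.10 summarises AEs leading to dose reduction in the 28-week period without a TEAE limit.

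The protocol's TEAE definition (16.9.1) uses onset alone: "an adverse event that starts on or after the date of first dose of IMP in the extension study". The SAP widened it to include worsening, but no further.

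**The concern.** Safety and tolerability is the primary objective of both periods, and the table of AEs leading to withdrawal is one of its central displays. A reader expects it to show why patients stopped treatment in that period. Under these rules it shows only stops caused by events that began or worsened in that period.

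Patients with ongoing events can enter. Exclusion 7 in Protocol 5.3 removes a patient only if "The patient has a moderate or severe on-going adverse event from the lead-in study considered a potential safety risk by the investigator". Mild events, and moderate or severe ones not judged a risk, may be carried across Baseline II. Substudy exclusion 9 is worded in the same way for Baseline III.

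The substudy is the more sensitive case. Protocol 3.2 presents its design as allowing safety to be compared within a patient before and after memantine is added. Placing a memantine-period withdrawal by onset puts it on the before side.

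**Working it through.** **Step 1. Trace the rules.** Intensity is unchanged except in the last row.

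| Event | Preferred-term withdrawal summary (11.1.9) | Disposition (6.2) |
|---|---|---|
| Ongoing at Baseline II; withdrawal in the 28-week period | Absent: not a TEAE | Counted in the 28-week period |
| Starts after Baseline II and by Baseline III; withdrawal in the memantine period | In the initial-period table; absent from the memantine table | Counted in the memantine period |
| Ongoing at Baseline II; withdrawal in the memantine period | Absent from both tables | Counted in the memantine period |
| Ongoing at the period's baseline, then worsens in that period before withdrawal | Present, correct period | Counted in that period |

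In the first row, SAP 11.1.4 sends the event to the lead-in report. Entry requires completion of lead-in Visit 7 (inclusion criterion 1), so the patient is a completer there and the event cannot appear as a cause of withdrawal. In the second row, the initial-period table shows an AE withdrawal for a patient who had to complete that period to enter the substudy. An SAE that becomes serious after the relevant baseline at unchanged intensity follows the same paths in SAP 11.1.8.

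**Step 2. Check the other AE outputs.** The overview in 11.1.5 does not say treatment-emergent, but 11.1.4 splits all AE tables and listings by period and sends unchanged carried-over events to the lead-in report. Whether the overview includes them is therefore unclear. The listings in 11.1.8 and 11.1.9 include them if read literally, but the same period split applies.

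**Step 3. Reproduce the plan's substudy limits** (SAP section 15). The exact one-sided 90% upper limit for x events in n = 100 is the 0.90 quantile of Beta(x+1, 100−x).

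| x | 0 | 1 | 2 | 3 | 4 | 5 | 10 |
|---|---|---|---|---|---|---|---|
| Computed, % | 2.28 | 3.83 | 5.23 | 6.56 | 7.83 | 9.08 | 14.99 |
| Plan, % | 2.3 | 3.9 | 5.3 | 6.6 | 7.9 | 9.1 | 15.0 |

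The plan's figures reproduce to within 0.1 point (rounded up).

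**Step 4. Size in the substudy.** One misplaced withdrawal is 1/100 = 1 percentage point. On the plan's table, 0 instead of 1 event lowers the upper limit from 3.9% to 2.3%. As an illustration with assumed counts, suppose 5 patients withdraw for AEs and 1 or 2 of those events began by Baseline III without worsening. The memantine table then shows 4 or 3, and the limit reads 7.9% or 6.6% instead of 9.1%.

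**Step 5. Size in the main period.** The documents give no rate of events ongoing at Baseline II and no share of withdrawals due to them, so no count can be derived. The plan's own figures are 1770 × 0.85 = 1504.5 lead-in completers and 1504.5 × 0.85 = 1278.8 extension completers (stated as 1280). The difference, about 226, has to cover ineligibility and withdrawal for every reason.

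**The case against.** The strongest reply is that little is actually lost. Disposition counts each patient in the right period by reason, the withdrawn patients are listed, and all AEs leading to withdrawal and all SAEs are to be listed. This stands in part. A reader might infer that the events vanish from the extension's reporting, and the documents do not support that. What is missing or misplaced is the preferred-term (and SOC) row.

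Second, an event that moves from tolerable to causing withdrawal or hospitalisation will often be regraded. Intensity changes are logged (Protocol 10.3), so it would then be captured. This also stands, and it confines the gap to events of unchanged recorded intensity.

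Third, an event that predates memantine and did not worsen is weak evidence about memantine. That is fair as a point about causality. It does not justify showing the withdrawal in a period the patient completed.

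Two stronger readings are tempting:
- **Bias between former idalopirdine and former placebo patients.** A reader might infer this from carried-over drug-related events such as raised transaminases. The documents give no group-specific rate of ongoing events. Exclusion 10 bars ALT or AST above 1.5 times the upper limit on the latest available sample, well below the multiples in the liver withdrawal criteria (Protocol 5.4). In phase II the elevations appeared around week 8 and later fell towards the reference range (Protocol 1.1.3.3), whereas Baseline II is at week 24.
- **A count of lost withdrawals from the phase II AE-withdrawal rates of 7.5% and 15%.** Applying 15% to 1504.5 gives about 226, the plan's whole allowance for ineligibility and all non-completion. Any carry-over share applied to it would be a guess.

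**Conclusion.** The point holds for the preferred-term and SOC summaries in SAP 11.1.8 and 11.1.9. An unchanged event carried over Baseline II that leads to withdrawal in the 28-week period is absent. One that starts by Baseline III and leads to withdrawal in the memantine period sits in the wrong table. The tables may then disagree with disposition, and possibly with the overview. The dose-reduction summary shows that the SAP can report by action without a TEAE limit.

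The number of patients affected cannot be computed. It is probably small in the main period, because worsening events are captured. In the substudy each case is 1 percentage point, assuming about 100 treated patients. No claim of bias between lead-in groups is supported. This is a limited reporting defect with an inexpensive remedy.

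**What to change.** - **SAP 11.1.9:** summarise all AEs leading to withdrawal by preferred term in the period in which the patient withdrew, whatever the onset. Keep the TEAE-only count as a subset row.
- **SAP 11.1.4:** exempt these events from the note that confines unchanged events to the lead-in report.
- **SAP 11.1.5 and the listings:** state that the same rule applies.
- **SAP 6.2:** reconcile the AE-withdrawal count with disposition in each period and explain any difference.
- **SAP 11.1.8:** apply the same rule to SAEs, by the period in which the event became serious, if that date can be obtained from the SAE report. The AE fields listed in Protocol 10.3 do not include it. Otherwise add a count of SAEs with earlier onset.

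For withdrawals the cost is SAP wording and a changed selection rule. Withdrawal date and action taken are already collected, and ongoing lead-in events are transferred to the eCRF (Protocol Panel 2, footnote j). The downsides are a slightly higher AE-withdrawal percentage and some events appearing in both the lead-in and extension reports, which a footnote should state.
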